### 6.3 Case Definitions Co-morbidities

Subjects with the following selected co-morbidities are at increased risk of severe illness from COVID-19 and will be included in the trial. Life expectancy of at least 1 year as per the Investigators' assessment is required for inclusion of the subject into the trial.

- **Chronic kidney disease:** Kidney function will be ascertained from the serum creatinine measurement within the last 6 months, converted into estimated glomerular filtration rate (eGFR) using the Chronic Kidney Disease Epidemiology Collaboration (CKD-EPI) equation, with impaired kidney function defined as eGFR <60 mL/min/1.73m^2.
  - Mild chronic kidney disease is defined as an eGFR between 60-89 mL/min/1.73 m^2.
  - Moderate chronic kidney disease is defined as an eGFR between 31-59 mL/min/1.73 m^2 with stable therapy and good maintenance over at least 6 months [23].

- **Chronic obstructive pulmonary disease** (COPD) (including emphysema and chronic bronchitis).
  - Mild COPD with or without cough or sputum production is defined as forced expiratory volume in 1 second/forced vital capacity (FEV1/FVC) <0.7 and FEV1 ≥80% predicted.
  - Moderate COPD with or without cough or sputum production is defined as FEV1/FVC <0.7 and FEV1≥50%, but <80% predicted with stable treatment (GOLD Criteria for COPD severity).
- **Obesity** with body mass index >32 kg/m^2.
- **Chronic cardiovascular disease** (heart failure, structural heart disorder, coronary artery disease, cardiomyopathies, arterial hypertension), including the following:
  - Heart failures (according to New York Heart Association [NYHA] classification [24]):
    - Class I: No limitation of physical activity. Ordinary physical activity does not cause undue fatigue, palpitation, dyspnea (shortness of breath).
    - Class II: Slight limitation of physical activity. Comfortable at rest. Ordinary physical activity results in fatigue, palpitation, dyspnea (shortness of breath).
  - A structural heart disorder
    - without symptoms
    - with symptoms.
  - Coronary artery disease:
    - Mild with metabolic equivalent threshold (MET) <3, stable with medication.
    - Moderate with MET >3 – 5.9, stable with medication.
  - Cardiomyopathies of non-infective and metabolic origin:
    - Mild with MET <3, stable with medication.
    - Moderate with MET >3 – 5.9, stable with medication.
  - Hypertension (National Institute for Health and Care Excellence [NICE] categorization [26]):
    - Stage 1 hypertension: Clinic blood pressure ranging from 140/90 mmHg to 159/99 mmHg and subsequent ambulatory blood pressure monitoring (ABPM) daytime average or home blood pressure monitoring (HBPM) average blood pressure ranging from 135/85 mmHg to 149/94 mmHg.

 MET is defined as the amount of oxygen consumed while sitting at rest and is equal to 3.5 mL O2 per kg body weight/min and is roughly equivalent to the expenditure of 1 kcal per kilogram of body weight per hour; 1 MET is the rate of energy expenditure while at rest. A 4 MET activity expends 4 times the energy used by the body at rest. Light MET is <3, moderate is 3 to 5.9 and vigorous is ≥6.0. MET 1 can take care of him/herself and may not maintain themselves and gets constraints on exertion. MET 4 can climb a flight of stairs or walk up a hill and can participate in other strenuous activities; >2-3 METs is fit normal person with well controlled with medication [25].

- Stage 2 hypertension: Clinic blood pressure of 160/100 mmHg or higher but less than 180/120 mmHg and subsequent ABPM daytime average or H BPM average blood pressure of 150/95 mmHg or higher.
- **Chronic HIV infection with stable aviremia (<50 copies/mL) and CD4 count >350/mL** as documented by blood samples taken within 12 months before enrollment. Viral load <50 copies/mL over 12 months with transient changes of 50-350 copies/mL is allowed.
- **Type 2 diabetes mellitus**, controlled with medication [HbA1c <58 mmol/mol (7.45%)]; [(HbA1c in % - 2.15) x 10.929 = HbA1c in mmol/mol].
- **Subjects with a renal transplant** at least a year ago under stable conditions for at least 6 months with medications, categorized as low risk of rejection.

Following inclusion of 25 cases of mild to moderate conditions under chronic kidney disease, COPD, chronic cardiovascular disease and diabetes mellitus, more severe conditions can be included into the trial upon iSCR and DSMB Chair approval and subjected to the clinical Investigator's decision (refer to Section 5.1 for details on the stratification based on co-morbidities).

- Under cardiovascular disease, the following cases can be included:
  - Heart failures (according to NYHA classification [24]) Class III: Marked limitation of physical activity. Comfortable at rest. Less than ordinary activity causes fatigue, palpitation, or dyspnea (shortness of breath).
  - Coronary artery disease: Severe with MET >6, stable with medication.
  - Cardiomyopathies of non-infective and metabolic origin: Severe with MET >6, stable with medication.
  - Hypertension (NICE categorization [26]): Stage 3 or severe hypertension: Clinic systolic blood pressure of 180 mmHg or higher or clinic diastolic blood pressure of 120 mmHg or higher.
- Under diabetes mellitus, cases of uncontrolled diabetes mellitus with recent HbA1c of >59 mmol/mol (7.45%) with medication can be included. For uncontrolled diabetes mellitus, HbA1c should be within <10% variation and the subject should not have any history of diabetic ketoacidosis or episode of severe symptomatic hypoglycemia within the past 3 months.

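### Protocol 6.3 and SAP 10.4 grade coronary artery disease and cardiomyopathy by MET in reverse, so the severity summary in SAP 12.2 would report the most limited of these subjects as mild

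*Protocol*

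**What the plan says.** Protocol 6.3 lists five cardiovascular subtypes: heart failure, structural heart disorder, coronary artery disease, cardiomyopathy and hypertension. Coronary artery disease and cardiomyopathy are the two graded by MET. Each has the same first two classes: "Mild with MET <3, stable with medication" and "Moderate with MET >3 – 5.9, stable with medication". The third class, which could be enrolled only after the safety review of the first 25 subjects, reads "Coronary artery disease: Severe with MET >6, stable with medication" and "Cardiomyopathies of non-infective and metabolic origin: Severe with MET >6, stable with medication". The synopsis and SAP 10.4 repeat these definitions.

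The footnote to the same list, printed in both documents, gives activity bands: "Light MET is <3, moderate is 3 to 5.9 and vigorous is ≥6.0". It then describes people by their MET level: "MET 1 can take care of him/herself and may not maintain themselves and gets constraints on exertion". A person at MET 4 is said to manage stairs, hills and other strenuous activity, and a person above about 2 to 3 METs is called fit and well controlled.

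Heart failure, in the same list, is graded by NYHA. It starts at "Class I: No limitation of physical activity" and reaches "Class III: Marked limitation of physical activity" for the class held back until after the review.

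SAP 12.2 says that co-morbidities will be summarised by severity and that data on the primary co-morbidities will be listed. SAP Appendix 4 lists the outputs kept in the abbreviated scope, including Table 14.1.2.1 (demographics) and Listing 16.2.4.3.4 (cardiovascular co-morbidity).

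**The concern.** The three MET classes appear to be the footnote's light, moderate and vigorous activity bands relabelled as mild, moderate and severe disease. Vigorous activity is something a fitter patient can do, so using the band as a disease grade turns the scale around: the least capable patients become mild and the most capable become severe.

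Two things depend on the labels. The first is description. If the severity summary in SAP 12.2 is built from SAP 10.4, a reader of the report gets the severity mix of these two subtypes in the wrong order. Protocol 5.3 presents well-characterised co-morbidities as the reason for running this trial alongside the other Phase 3 trials, so that description matters. The second is the account of the first-25 restriction in Protocol 5.1, which admitted only mild to moderate cases before the iSRC and DSMB Chair review. As printed, it would admit MET below 3 and hold back only MET above 6.

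**Working it through.** The plan gives no figure to reproduce. The check is one of direction, made against the documents' own text.

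**Step 1. Set the scales side by side.**

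| Label in Protocol 6.3 / SAP 10.4 | MET range | Footnote's activity band | Footnote's description of people at or near that level | NYHA counterpart in the same list |
|---|---|---|---|---|
| Mild | <3 | light, <3 | MET 1: constrained on exertion | Class I: no limitation |
| Moderate | >3 to 5.9 | moderate, 3 to 5.9 | MET 4: stairs, hills, strenuous activity | Class II: slight limitation |
| Severe | >6 | vigorous, >=6.0 | above about 2 to 3: already fit and well controlled | Class III: marked limitation |

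The MET classes follow the activity bands almost exactly. They run against the footnote's description of people and against NYHA.

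**Step 2. Convert to oxygen uptake.** The footnote gives 1 MET = 3.5 mL O2/kg/min.

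- Upper limit of mild: 3 × 3.5 = 10.5 mL/kg/min.
- The footnote's stair-climbing level: 4 × 3.5 = 14 mL/kg/min.
- Lower limit of severe: 6 × 3.5 = 21 mL/kg/min.

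Every subject classed as mild is below the stair-climbing level. Every subject classed as severe is above it by more than half (21/14 = 1.5).

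**Step 3. Try the other reading of MET.** The definitions do not say whether MET means the highest level the subject can reach or the level at which symptoms begin. If it means the onset of symptoms, symptoms below 3 METs are worse disease than symptoms above 6. Both readings give the same reversed order.

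**Step 4. Check coverage.** The classes are <3, >3 to 5.9, and >6. A value of exactly 3 fits none of them, and neither does any value above 5.9 up to and including 6. The footnote's own bands do include 3 and 6.0.

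**Step 5. Trace where the labels are used.** SAP 12.2 plans the severity summary. SAP 12.7 marks analyses outside the abbreviated scope with an asterisk, but 12.2 carries no such mark and nothing else expressly withdraws the summary. Appendix 4 has 9 + 5 + 1 + 16 + 7 = 38 table titles (14.1, 14.2, 14.3.1, 14.3.2, and 14.3.3 with 14.3.4). None names co-morbidity severity; the three that mention severity concern adverse events. The rows could sit in Table 14.1.2.1, but the layouts are in separate shells (SAP 10.0). SAP 9.4, 12.0 and 12.7 report safety and immunogenicity overall and by co-morbidity, not by severity within a co-morbidity.

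**The case against.** The reversed direction is hard to dispute; the case on the other side is about consequence.

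- *The affected output may not exist.* SAP 6.3 says Appendix 4 holds the planned outputs, and no title there names co-morbidity severity. The table shells and the eCRF are not among the documents. This stands as a limit. It does not clear the plan, because SAP 12.2 still states the summary and SAP 10.4 still supplies the definition.
- *Listings show the underlying data anyway.* Listing 16.2.4.3.4 gives subject-level data, but whether it holds a numeric MET is not stated. If it shows only the class, a reader would turn to SAP 10.4 to interpret it and be misled in the same way.
- *The gate.* A reader might infer that the most limited coronary and cardiomyopathy patients were in fact vaccinated before the safety review. The documents do not support that. None shows that any subject with MET below 3 was enrolled, or how sites applied the labels. Protocol 5.1 required disease that was controlled and stable in the Investigator's judgment, and each MET class adds stability on medication. Sites may have used clinical sense instead of the printed numbers. Enrolment is closed, so an SAP change cannot alter who entered.
- *A footnote alone would do.* Where only a class was recorded, it would. Where a numeric MET exists, there is no reason to pass it through reversed cut points and then apologise for the result.

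**Conclusion.** The definition is wrong as written, and the consequence is minor. For coronary artery disease and cardiomyopathy, Protocol 6.3 and SAP 10.4 order severity opposite to functional capacity and leave small gaps at MET 3 and just below and at MET 6. The severity summary stated in SAP 12.2, built from these definitions, would call the most limited of these subjects mild.

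The size is two of five cardiovascular subtypes in one descriptive baseline output. The documents give no count for these subtypes; they are some unstated part of the 129 enrolled. The reporting consequence assumes that the summary is produced and that recorded or derived severity follows the printed cut points. Neither can be confirmed from the documents.

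A reader might infer more: that safety or immunogenicity results are distorted, or that the other severity scales are suspect too. Neither follows. No endpoint or sample-size figure uses these labels, and the NYHA and hypertension classes run in the right direction. Swapping mild and severe in the recorded data would also go too far, since a site that judged severity clinically may already have recorded it correctly.

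**What to change.** In SAP 10.4 and 12.2, state that mild, moderate and severe will not be derived from the printed MET cut points for coronary artery disease and cardiomyopathy.

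- Where a numeric MET was recorded, tabulate <3, 3 to <6 and >=6, and state that a lower MET means worse capacity. These bands also close the gaps.
- Where only a class was recorded, show it as recorded, with a footnote that the protocol definition runs opposite to functional capacity. Do not swap labels or assign a numeric MET.
- Put the same footnote on Listing 16.2.4.3.4 and in the abbreviated CSR.

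The grading of the other subtypes and co-morbidities is not touched.

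The cost is SAP wording, at most a few relabelled rows in one descriptive table, one footnote used in three places, and a check of whether the eCRF holds a numeric MET. No new subject data are needed.

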## 6.4 Vaccine Delay Recommendations

After enrollment, subjects may encounter clinical circumstances that warrant a delay of trial vaccine administration. These situations are listed below:

- Subjects with a clinically significant (Grade  $\geq 2$ ) active infection or other acute disease (as assessed by the Investigator and SARS-CoV-2 infection is either not clinically suspected or testing is negative) or body temperature  $>38.0^{\circ}\text{C}$  ( $>100.4^{\circ}\text{F}$ ), within 3 days of intended trial vaccination. Further dose administration should be delayed until the active infection or other acute disease has recovered to Grade  $\leq 1$  or the subject's body temperature has decreased to  $\leq 38.0^{\circ}\text{C}$  ( $\leq 100.4^{\circ}\text{F}$ ) for at least 3 days, if this still allows to vaccinate the subject as per the predefined interval. Body temperature should be measured orally and by using the thermometer provided to the subject at Visit 1.

- For subjects who develop laboratory-confirmed COVID-19 after the first dose but prior to receiving the second dose of CVnCoV, once the subject has recovered from COVID-19, the subject can be vaccinated with the second dose of CVnCoV, following two weeks of complete recovery if within the per protocol defined allowed time windows as specified in Table 1.
- Subjects who took antipyretic medication within 8 hours before intended trial vaccination (this is not applicable to the intake of low dose acetylsalicylic acid taken for prevention of cardiac disease).

In case of delay, the vaccination should take place within the allowed time windows specified in Table 1.

In case of any complications, the subsequent vaccination may be stopped or delayed.

## 6.5 Failure to Meet Eligibility Criteria

The Investigator must account for all subjects who sign an ICF. If the subject is found to be not eligible (i.e., did not meet all inclusion criteria or met one or more exclusion criteria), the Investigator should document this in the subject's source data and electronic case report form (eCRF).

Re-doing the full assessments for eligibility assessment as per Table 1 or re-testing (i.e., re-doing a single assessment) is allowed if the reason for ineligibility is a transient event.

An example of a condition under which re-assessment may be considered includes:

- Subjects who required treatment for an acute illness that resolved (e.g., a urinary tract infection) may be re-assessed once the illness resolved or the medical problem stabilized.

An example of a condition under which re-testing may be considered includes:

- Subjects who have clinical laboratory test value(s) that are not in line with the medical history and clinical evaluation of the subjects may be re-tested to confirm the value of the tests, if still allowed within the enrollment period (Day -7 to Day 1). If not feasible, the subject should be re-assessed for eligibility.

## 7 TRIAL VACCINE

### 7.1 Trial Vaccine Administration

#### 7.1.1 Description of the Trial Vaccine

CVnCoV is an investigational LNP-formulated RNActive® SARS-CoV-2 vaccine containing 12 µg mRNA. The IMP is composed of the active pharmaceutical ingredient, an mRNA that encodes the stabilized full-length S protein, and 4 lipid components: cholesterol, 1,2-distearoyl-sn-glycero-3-phosphocholine (DSPC), PEG-ylated lipid, and a cationic lipid.

#### 7.1.2 Dosing and Administration

All subjects will be administered a first vaccine dose of CVnCoV on Day 1 and a second vaccine dose on Day 29.

Injections must be performed IM by needle in the deltoid area (preferably in the non-dominant arm).

CVnCoV is intended strictly for IM injection and must not be injected subcutaneously, intradermally, or intravenously. The instruction for injection described in the trial-specific pharmacy manual must be followed. An intravascular injection is highly unlikely at this site due the lack of larger blood vessels.

Subjects should be observed for 1 hour following each vaccination. Since there is a theoretical risk of anaphylactic reactions, the vaccine must only be administered if emergency equipment for the treatment of anaphylactic reactions (intravenous fluids, corticosteroids, H1 and H2 blocking agents, epinephrine, equipment for cardiopulmonary resuscitation) is readily available, as presented in

1. Review and provide a signature as approval of the content of the clinical trial report (to be reported by the coordinating Investigator).

**Appendix 2.** If anaphylaxis or severe hypersensitivity reactions occur following IMP administration, no further doses should be given.

### 7.2 Preparation/Handling/Storage/Accountability

#### 7.2.1 Preparation

Mixing of CVnCoV and 0.9% NaCl to produce dosing solutions for IM injection will occur according to the handling manual provided by CureVac AG.

#### 7.2.2 Product Storage and Stability

CVnCoV is presented as an aqueous solution and stored below -60°C.

#### 7.2.3 Accountability

It is the responsibility of the Investigator to ensure that the current and accurate records of trial supplies received, stored, and dispensed at the site are maintained using appropriate forms according to applicable regulations and guidelines. The trial supplies must be stored under the recommended storage conditions and locked with restricted access (refer to the pharmacy manual). Authorized personnel must dispense the vaccine

at the trial site and in accordance with the protocol and applicable regulations and guidelines.

IMP accountability and inventory logs must be kept up-to-date at the trial site with the following information:

- Dates and quantities of CVnCoV received from CureVac.
- Unique subject identifier.
- Date and quantity of CVnCoV dispensed to each subject.
- Initials of the person preparing the dose.
- Initials of the person administering the vaccine.

These logs must be readily available for inspections and are open to regulatory inspection at any time.

### **7.3 Randomization and Blinding**

Not applicable, since this is an open-label, single-arm trial.

### **7.4 Vaccine Compliance**

The Investigator will record all CVnCoV injections administered in the subject's eCRF page.

### **7.5 Misuse and Overdose**

**Definition misuse:** Situations where the trial vaccine is intentionally and inappropriately used not in accordance with the protocol dosing instructions or authorized product information.

**Definition overdose:** Administration of a quantity of the trial vaccine given per administration or cumulatively which is above the maximum recommended dose according to the protocol dosing instructions or authorized product information.

No toxic effects are expected from current clinical and non-clinical experience. Possible local reactions (pain) or systemic AEs (fever, headache, fatigue, chills, myalgia, arthralgia, nausea/vomiting, and diarrhea) should be treated symptomatically with physical measures, paracetamol or non-steroidal anti-inflammatory drugs.

### **7.6 Concomitant Therapy and Vaccines**

Concomitant medication and vaccines including the reason for administration must be recorded in the subject's eCRF.

For additional information, refer to Section 6.2.

### **7.7 Therapy Leading to Discontinuation**

If a subject requires therapy listed as an exclusion criterion in Section 6.2 and which cannot be delayed, discontinuation would be considered to ensure integrity of the trial data, following individual case review, but safety follow-up until 12 months after the last dose of CVnCoV should be pursued.

## **7.8 Treatment After the End of Trial**

This trial will investigate a prophylactic vaccine and therefore post-trial care is not applicable.

## 8 DISCONTINUATION/WITHDRAWAL CRITERIA

Participation in the trial is strictly voluntary. A subject has the right to withdraw from the trial at any time and for any reason. The Investigator has the right to withdraw a subject from further trial vaccine administration and/or the trial if this is considered in the subject's best interest or as a result of a protocol deviation.

For discontinuations due to an AE, every effort should be made to document the outcome of the event.

Subjects who received at least 1 dose of trial vaccine will be encouraged to continue participation until the end of the trial for safety assessments. Assessments of solicited AEs for the second dose will not be necessary if a subject received only 1 dose. Overall, only relevant visits need to be conducted for any subjects who prematurely discontinue from trial product administration. Blood samples for immunogenicity assessments may be taken at the Investigator's discretion.

### 8.1 Discontinuation of Trial Vaccine Administration

The primary reason for discontinuation of further administrations of trial vaccine doses will be recorded in the subject's eCRF according to the following categories:

- Consent withdrawal by the subject.

The reason for withdrawal, if provided, should be recorded in the eCRF.

Note: All attempts should be made to determine the underlying reason for the withdrawal and, where possible, the primary underlying reason should be recorded (i.e., withdrawal due to an AE should not be recorded in the "voluntary withdrawal" category).

- AE (including known side effects of the trial vaccine).

If discontinuation is due to an AE possibly related to the trial vaccine or trial procedures, the subject must be followed up by additional examinations according to the medical judgment of the Investigator until the condition is resolved or the Investigator deems further observations or examinations to be no longer medically indicated.

- Change in the subject's overall medical status prohibiting further participation.
- Pregnancy (see Section 9.1.2).

Any subject who, despite the requirement for adequate contraception, becomes pregnant during the trial will not receive further trial vaccine doses. The site should maintain contact with the pregnant subject and complete a "Clinical Trial Pregnancy Form" as soon as possible. In addition, the subject should be followed up until the birth of the child, or spontaneous or voluntary termination. When pregnancy outcome information becomes available, the information should be captured using the same form. The subject should be reported as an IMP discontinuation and the reason (i.e., pregnancy) should be given.

- SARS-CoV-2 infection, virologically confirmed by positive RT-PCR test (as specified in Table 1).

Note: Subjects who develop laboratory-confirmed COVID-19 after the first vaccine dose administration should only receive the second vaccine dose 2 weeks after getting fully recovered and if it falls under the time windows (see Section 6.4).

- Trial terminated by the Sponsor (in which case the minimum safety follow-up of 1 year after the last trial vaccine dose would be performed).
- Major protocol deviation.
- Wants to receive authorized/licensed vaccine.
- Other.

Note: The specific reasons should be recorded in the “specify” field of the eCRF.

